### 7.3. Interventions

#### 7.3.1. Methylnaltrexone dosage and treatment duration

To ensure standardization of the protocol, patients with AP will be treated with methylnaltrexone or placebo intravenously for the first 5 days of admission and assessments of endpoints will be done at fixed time points during this period. The dosage will be weight adjusted. Thus, 0.15 mg/kg methylnaltrexone or a corresponding volume of matching placebo (Ringer's lactate) will be dissolved in 1000 mL Ringer's lactate solution and given as a continues infusion over 24 hours using an infusion pump. In accordance with the summary of product characteristics for methylnaltrexone, a 50 % dose reduction will be made for patients with an eGFR below 30 ml/min/1,73m^2. the continuous infusion of study medication will be started no later than 24 hours after preparation. This will be ensured by keeping detailed record on the time of preparation

as well as time of infusion start. As methylnaltrexone is sensitive to light, the solution will be kept protected from light from the time of preparation until the time of infusion start. Two persons trained in the protocol and delegated to do so, will prepare the solution of study medication together. This will be done with one person assisting virtually in exceptional cases.

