## 7.5. Participant timeline

### 7.5.1. Study days

A detailed description of the study procedures is illustrated in Table 1. Patients will be evaluated daily during admission by medical personnel and treated in agreement with the IAP/APA evidence-based guidelines for the management of AP (2). As part of the study, they will receive daily infusions with methylnaltrexone or matching placebo, and have the following examinations performed: i) clinical outcome and patient symptoms will be evaluated by means of both well-validated questionnaires and information from the patient's medical records (see section 9.1.2.), ii) the PASS score will be obtained daily and used to document the primary endpoint 48 hours after randomization, iii) blood samples (including C-Reactive Protein (CRP), interleukin (IL)-6, IL-8, IL-18, tumor necrosis factor alpha (TNF- $\alpha$ ) and cluster of differentiation 163 (CD163)) will be drawn

daily with the purpose of evaluating the systemic inflammatory response, and iv) an abdominal contrast-enhanced CT study will be performed at inclusion and after conclusion of treatment at day 5 (+/- 1 day) to document the presence and extent of pancreatic inflammation, fluid collections and necrosis according to the definitions given in the revised Atlanta criteria (20). As an integrated part of the CT exam at day 5 (+/- 1 day) patients will undergo assessment of the colon/gut transit time using radiopaque markers given orally in the morning on day 3 up to the planned CT exam. Finally, the intestinal permeability will be evaluated by a polyethylene glycol (PEG) 400/4000 test (see section 9.1.5.) 48 hours after randomization. At hospital discharge, patients are invited for a follow-up visit on day 14 (+/- 2 days) after randomization where the outcomes assessed during hospital admission (blood test and questionnaires including the PASS score) will be reassessed. Patients ready for discharge prior to completing five days treatment with methylnaltrexone will be handled according to the following:

- < 48 h of treatment: All data collection will be terminated upon discontinuation of the study medication and participant is regarded as dropout.

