### 9.3. Statistical methods

A repeated measures linear mixed effects model will be used for the primary analysis and will include terms for treatment group, assessment time point (day after randomization), and the interaction of treatment with assessment time point. Summary statistics and trend curves of PASS scores will be provided for the individual time points, and the difference in PASS scores between groups 48 hours after randomization is considered the primary efficacy parameter. Subgroup and covariate analyses will be performed if applicable and in case differences in patient subgroups deemed clinically relevant are evident. The primary analysis will be by intention to treat and in case of early hospital discharge or other reasons for missing values, the Last-Observation-Carried-Forward method will be employed. Trends in PASS and other secondary endpoints assessed consequently during the treatment period (biochemical tests and clinical outcome parameters) are analyzed using linear random-effects models and results presented as fitted trend curves. Outcomes assessed at single time points (baseline characteristics, CT features and gut permeability) are compared using Student's t-test or non-parametric analysis for continues data as appropriate. Binary outcomes will be analyzed using Fisher's exact test. All secondary endpoints will be analyzed by per-protocol.

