2.5.1. Primary Endpoint

The primary endpoint will be assessed 48 hours after randomization.

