6.3. Major Protocol Deviations

It is expected that a proportion of the patients included into the study, will recover before 5 days have passed and thus be discharged before completing the study protocol. In case of early discharge, data handling of both primary and secondary outcomes be stratified according to table 2:

< 48 hours of treatment	All data collection will be terminated upon discontinuation participant is regarded as dropout.
\geq 48 hours of treatment, but discharge before day 5	Participant will be lost to follow-up on the following outcomes: daily PASS scores, blood samples, vital signs. The participant will be asked to complete questionnaires at home, and they will be offered a follow-up CT scan in an outpatient setting on day 5 (+/- 1 day). Furthermore, they will be invited to participate in the 14-day follow-up and mortality will be registered retrospectively.

Table 2

For the statistical analyses, the Last-Observation-Carried-Forward method will be employed in case of early hospital discharge or other reasons for missing values. We expect most missing values to be a consequence of early discharge (~ recovering early from their disease) and thus the Last-Observation-Carried-Forward method will reflect this by carrying forward a value corresponding to low disease activity after discharge, which we find to be a fair assumption. If this is not the case, e.g. if a lot of missing values are due to severe disease, we will consider using other methods for imputation of missing values.

7. Implementation of Analysis Plan

A monitor will be allocated from the good clinical practice (GCP) unit at Aarhus and Aalborg University Hospitals, and the responsible monitor will contact and visit the principal investigator on a regular basis. The monitor will be authorized to inspect the different study records (CRFs,

Aalborg, Denmark

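### LOCF can fill a missing 48-hour PASS only with an in-hospital baseline or 24-hour score, so the SAP's reason for LOCF is not ensured at the primary time point, and its fallback names no trigger or method

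*SAP*

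**What the plan says.** The primary endpoint is fixed in time: "The primary endpoint will be assessed 48 hours after randomization" (SAP 2.5.1). Protocol 7.5.1 agrees: "the PASS score will be obtained daily and used to document the primary endpoint 48 hours after randomization". Protocol Table 1 places PASS at baseline, 24±2 h, 48±2 h, then daily to 120 h and at day 14.

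For patients ready for discharge with less than 48 hours of treatment, Protocol 7.5.1 says: "All data collection will be terminated upon discontinuation of the study medication and participant is regarded as dropout". SAP Table 2 has the same rule. Neither document schedules a PASS at discharge.

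Protocol 9.3 sets the imputation rule for the primary analysis: "in case of early hospital discharge or other reasons for missing values, the Last-Observation-Carried-Forward method will be employed". It gives no reason, and Protocol 9.3.2 leaves missing data to the SAP. SAP 6.3 repeats the rule ("For the statistical analyses, the Last-Observation-Carried-Forward method will be employed in case of early hospital discharge or other reasons for missing values") and justifies it as "carrying forward a value corresponding to low disease activity after discharge, which we find to be a fair assumption". It then allows for failure of that assumption: "if a lot of missing values are due to severe disease, we will consider using other methods for imputation of missing values".

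SAP 6.1 specifies a repeated-measures mixed model with baseline PASS as a covariate. If that is significant, a Bonferroni-corrected t-test or a Mann-Whitney test at 48 hours follows. SAP 2.5 analyses the primary outcome by intention to treat. It also names earlier discharge of methylnaltrexone patients, and stopping because of side effects, as possible causes of imbalance between the arms.

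**The concern.** LOCF is defended by what it does after discharge: a recovered patient goes home and a low score is carried to the later days. For a patient discharged on day 3 or 4, with a 48-hour score already recorded, that is reasonable for the daily secondary PASS scores. At the primary time point the carried value comes from before discharge, from the first day of a condition that changes fast. If PASS fell between that score and 48 hours, the carried value is too high. If the patient was worsening, it is too low.

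The two arms need not be affected equally, since SAP 2.5 itself expects that discharge and discontinuation may differ by arm. A carried score that is wrong in more patients of one arm than the other shifts the estimated 48-hour difference. The SAP's safeguard does not say how many missing values, or of what kind, would trigger a change, nor what method would then be used.

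**Working it through.** **1. The plan's own figure.** Inputs from SAP 3.1 and Protocol 7.6: difference 25, SD 40, 80% power, two-sided alpha 0.05.

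n = 2 × [40 × (1.960 + 0.842) / 25]² = 40.19, rounded up to 41 per group. The stated 41 is reproduced. With a t-test, power is 79.8% at 41 and 83.5% at 45 per group. The allowance is (45 − 41)/45 = 8.9%, or 4 patients per group.

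**2. What LOCF can carry to 48 hours.** Scheduled PASS before 48±2 h: baseline and 24±2 h, both in hospital. A missing 48-hour value is therefore filled with one of these two. For scale, entry requires at least two SIRS criteria in the preceding 24 hours, and each scores 25 PASS points. If two are still present at baseline they give 2 × 25 = 50 points, twice the target difference.

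**3. Size under assumed discharge.** The documents give no rate of missing 48-hour scores, so every input here is an assumption: 45 per group; placebo means 140/110/95/80 at 0/24/36/48 h; treatment effects 0/12/18.5/25; SD 40; correlations 0.6 (0–24), 0.55 (0–36), 0.5 (0–48), 0.8 (24–36), 0.6 (24–48), 0.8 (36–48). There were 10,000 simulated trials per model, each tested with one unadjusted t-test at 48 hours. This is not the gated procedure of SAP 6.1.

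Bias is approximately (active discharged × active overstatement − placebo discharged × placebo overstatement) / 45.

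- Model A, discharged if 24-hour PASS is below 45: 4.16 active and 2.34 placebo patients, overstatement 14.3 and −2.6 points. (4.16 × 14.3 + 2.34 × 2.6)/45 = 1.5 points. Simulated estimate 24.9 on full data, 23.5 with LOCF. Power 83.3% falls to 81.0%.
- Model B, discharged if an unrecorded 36-hour PASS is below 25: 4.45 and 1.80 patients, overstatement 42.9 and 30.0. (4.45 × 42.9 − 1.80 × 30.0)/45 = 3.0 points. Simulated estimate 25.0 on full data, 21.9 with LOCF. Power 83.7% falls to 79.1%.

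Totals discharged before 48 hours are 6.5 and 6.25 of 90. With scores floored at zero the bias is 0.9 points (A) and 2.2 points (B).

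**4. Direction.** With no treatment effect, Model A gives an LOCF difference of 0.0 and 5.3% rejections, but there discharge is balanced between arms by construction. Now assume no effect and 4 active against 0 placebo patients whose carried score is 50 points too low, as when patients stop treatment while worsening. The spurious difference is 4 × 50/45 = 4.4 points in favour of methylnaltrexone, and about 7% of trials reject.

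**5. The alternative.** Maximum likelihood on observed scores, with equal baseline means in the two arms, gives 24.9 in Model A and about 23.5 in Model B (true value 25). Power against baseline-adjusted LOCF is 89.3% v 89.7% in A and 89.1% v 88.2% in B.

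**The case against.** The strongest reply is that the effect is small and assumed. SAP 6.3 expects some patients to recover before 5 days, not before 48 hours, and entry requires predicted moderate or severe disease. Both models use up most of the 8-patient allowance and still give only 1.5 to 3 points. Where discharge follows a low 24-hour score, the SAP's reason largely holds: in Model A the carried placebo score is slightly too low. The alternative gains almost no power and remains biased in Model B. All of this stands, and it limits the point to a modest one. It does not supply a reason for LOCF at 48 hours, or content for the fallback.

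A reader might infer four stronger things that the documents do not support.

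- *That it is unsettled whether replaced patients stay in the analysis.* SAP 2.5 allows one exclusion from intention to treat: randomized but never treated. A patient treated for under 48 hours therefore stays in, and so does a treated replacement. Protocol 9.3.1 says when the trial ends; it does not define an analysis set.
- *That counting dropout in hours of treatment and the endpoint in hours from randomization discards primary data.* A patient with a 48-hour PASS but under 48 hours of infusion is replaced, yet the score exists, is not missing, and stays in. The only effect is one extra recruit. The statement that "the continuous infusion of study medication will be started no later than 24 hours after preparation" concerns preparation and says nothing about delay after randomization.
- *That the bias can only dilute.* Step 4 of the working shows otherwise.
- *That the open fallback invites a results-driven choice.* Protocol 9.3.2 and SAP 7 place the decision and the analysis before unblinding. It is a gap in specification only.

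**Conclusion.** The point holds in this form. At the primary time point LOCF can use only a baseline or 24-hour in-hospital score, the justification in SAP 6.3 does not ensure that such a score represents the 48-hour state, and the fallback is undefined. The first part follows from the schedule alone and needs no assumption.

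The size does rest on assumptions. With about 6 of 90 patients discharged before 48 hours and more of them on active treatment, the 25-point difference shrinks by about 1.5 to 3 points (6% to 12%) and unadjusted power falls by about 2 to 5 percentage points. The power figures describe a single t-test, not the two-stage test in SAP 6.1. The direction is not established: early recovery on methylnaltrexone dilutes the effect, while missing scores from worsening or side effects can exaggerate it. With few missing 48-hour scores, or similar errors in both arms, the bias is near zero. The change should be made before unblinding, but the trial does not stand or fall on it.

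**What to change.** In SAP 6.1 and 6.3 and Protocol 9.3:

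1. Fit the planned mixed model to observed PASS scores without LOCF. Put baseline among the repeated outcomes, with a common baseline mean, so that patients with only a baseline score stay in. Take the 48-hour treatment difference and its 95% CI from this model. This replaces the baseline covariate and the post-hoc test in SAP 6.1 and should be stated openly as a change.
2. Keep LOCF as a sensitivity analysis.
3. Replace the open-ended fallback with one prespecified delta-adjusted sensitivity analysis over a stated range, for example missing 48-hour values shifted by −25 to +25 points. The range borrows the planned difference and should be labelled an assumption. With 4 of 45 values missing in one arm, a 25-point shift moves the difference by 4 × 25/45 = 2.2 points.
4. In Protocol 7.5.1 and SAP Table 2, state that a participant who stops study medication but is still in hospital and has not withdrawn consent has the already scheduled 48-hour PASS recorded.

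A cross-reference from the replacement rules (Protocol 8.2, SAP 3.2) to the intention-to-treat rule in SAP 2.5 is optional.

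The cost is a SAP revision and a small protocol amendment, with no change in sample size. The model assumes data missing at random, which leaves some bias if discharge depends on unrecorded status (about 23.5 against 25 in Model B). There is little or no gain in power over baseline-adjusted LOCF. The gain is an estimate that does not depend on carrying an early score forward.
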